There is emerging research demonstrating that dopamine is critical to the consolidation and subsequent recall of fear extinction learning (Abraham et al. 2012; Haaker et al. 2013a; Hikind and Maroun 2008; Mueller et al. 2010). Rodent studies have demonstrated that dopamine antagonists delivered after fear extinction training lead to *increased* fear responding upon subsequent CS+ presentation, and that dopamine agonists delivered after fear extinction training lead to *decreased* fear responding upon subsequent CS+ presentations. Similarly, a recent study of healthy adult humans demonstrated that oral administration of 150 mg L-DOPA after fear extinction learning led to decreased fear responding, even when tested in a new context. Further, this study also found that resting-state functional connectivity, measured ~45 minutes after post-extinction learning L-DOPA administration, between the ventral tegmental area (VTA) and mPFC was correlated with magnitude of mPFC recruitment during recall of the fear extinction learning. This latter finding suggests that the mechanism by which L-DOPA boosts consolidation of fear extinction learning is through acutely reorganized dopaminergic resting-state networks. Indeed, other studies have demonstrated an acute effect of L-DOPA administration on resting-state functional connectivity within dopaminergic neural networks (Cole et al. 2013a; Cole et al. 2013b; Kelly et al. 2009). Thus, agents that increase dopamine transmission acutely during the post-extinction learning consolidation window, and thereby acutely altering organization of dopaminergic neural networks, show promise for boosting the consolidation of fear extinction memories and decreasing fear responding. It is well established that dopamine neurotransmission demonstrates a nonlinear inverted “U” shaped relationship with measures of performance (Cools and D’Esposito 2011). This line of research demonstrates an optimal level of dopamine neurotransmission, varying by the task, for achieving optimal performance. Similarly, human studies using L-DOPA demonstrate an inverted “U” shaped relationship between L-DOPA dose and measures of performance (Monte-Silva et al. 2010; Thirugnanasambandam et al. 2011).

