## **B. Specific Aims**

**Specific Aim 1: Test the degree to which endogenous and exogenous manipulations of dopamine neurotransmission affect fear extinction learning across multiple indices.** *Hypothesis:* L-DOPA dose will interact with dopaminergic gene score to predict fear extinction learning across indices.

**Specific Aim 2: Test the degree to which post-extinction functional connectivity within dopaminergic neural networks mediates the effect of dopaminergic manipulation on fear extinction learning.** *Hypothesis:* The L-DOPA x dopaminergic gene score will predict enhanced post-extinction dopaminergic functional connectivity, which in turn predicts enhanced fear extinction recall.

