### Data analysis.

*Primary Analytic Framework for Fear Extinction Effects.* The overall data analysis framework for Aim 1 fear extinction analyses consists of a 3 (group: placebo vs 100 mg L-DOPA vs 200 mg L-DOPA) x 2 (cue: CS+ vs CS-) x 2 (context: A [learning context] vs B [extinction context]) x 6 (dopamine gene score: 0 [low endogenous dopamine] – 5 [high endogenous dopamine]) mixed design focused on Day 2 fear responding. Preliminary analyses would test for any baseline

differences in fear responding or extinction learning on Day 1 and include these variables as covariates if needed. Analyses would also control for ancestry as well as other demographic or clinical variables should they differ between groups.

*Neural circuit ROI definition and extraction.* The neural circuit indices would be 6 *a priori* regions of interest (ROI) with anatomical coordinates defined from the recent literature (Delgado et al. 2008; Haaker, Gaburro, Sah, Gartmann, Lonsdorf, Meier, Singewald, Pape, Morellini, & Kalisch 2013a; Milad, Wright, Orr, Pitman, Quirk, & Rauch 2007; Phelps, Delgado, Nearing, & LeDoux 2004; Schiller et al. 2008) and include bilateral amygdala, bilateral hippocampus, ventromedial PFC, dorsal anterior cingulate cortex. Following standard preprocessing, first-level analyses conducted for each individual separately would consist of whole-brain GLMs, in which the task design (CS+ vs CS- during Context A vs B) is modeled as boxcar events convolved with a canonical HRF. The task design is regressed onto each voxel's timecourse within a GLM framework and using restricted maximum likelihood to account for serial correlation, resulting in a whole-brain spatial map indicating the degree to which each voxel responds to CS+ vs CS- during Context A vs B. The mean contrast values for CS+ vs CS- as a function of context is then extracted from the voxels within 6 mm spherical ROIs for the six ROIs. These analyses would provide six (for each ROI) indices of activation, calculated separately for each participant, that would be used in multivariate analysis of variance (MANOVA) analyses to define the impact of L-DOPA and dopamine gene score on consolidation of fear extinction learning.

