would define three regions-of-interest (ROIs) with which to calculate resting-state FC: 1) the substantia nigra/ventral tegmental area (SN/VTA; MNI X, Y, Z coordinates = -8, -18, -20 mm), a critical region of the dopaminergic midbrain, 2) the dorsal caudate (DC; MNI X,Y,Z coordinates =  $\pm 13, 15, 19$  mm), and the ventral (limbic) striatum (VS; MNI X,Y,Z coordinates =  $\pm 16, 12, -10$  mm). Consistent with our prior RSN FC analyses (Cisler et al. 2012; Cisler et al. 2013), we would characterize FC with these seed regions using the following approach within each individual separately. First, we would extract the first principal component timecourses of 6 mm spheres centered separately on the three ROIs. Second, the seed region timecourse would be regressed onto the timecourse of every other voxel (i.e., whole-brain analyses) using an autoregressive model (AFNIs 3dREMLfit) and using an *r*-to-*z* transformation to improve normality. This would result in a separate whole-brain spatial map, indicating its degree of FC with the seed region, for each ROI and each participant.

*Defining the effect of L-DOPA and dopamine gene score on striatal and mid-brain FC.* Between-group GLMs would analyze functional connectivity (FC) using a 3 (group: placebo vs 100 mg L-DOPA vs 200 mg L-DOPA) x 2 (cue: CS+ vs CS-) x 6 (dopamine gene score: 0 [low endogenous dopamine] – 5 [high endogenous dopamine]) between-subjects ANOVA in a whole-brain, mass univariate, approach. Covariates of non-interest would be included if the “urn” balanced randomization procedure should fail to match groups on demographic and clinical severity variables. Cluster-level thresholding would be used to correct for multiple comparisons. This approach would identify clusters of voxels where FC with the SN/VTA, DC, or VS differed significantly as a function of L-DOPA, dopamine gene score, or the interaction. This analysis establishes the engagement of the intermediate mechanism in the proposed conceptual model hypothesized to mediate dopamine neurotransmission’s pro-extinction effect.

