*Testing the effect of altered resting-state FC on fear extinction learning consolidation.* Following identification of regions where FC with the DC, VS, and SN/VTA differ as a function of the L-DOPA x gene score interaction, we would then test whether individual differences in FC within these clusters predict subsequent consolidation of fear extinction learning. That is, we would test whether the hypothesized intermediate mechanism (acute dopamine neurotransmission and downstream dopaminergic neural networks) is related to the ultimate mechanism of interest (fear extinction learning). Consolidation of fear extinction learning from Day 1 would again be tested using Day 2 fear expression indices in Context A and Context B (i.e., fear extinction learning recall test) using multimodal assessments (neural circuit indices, psychophysiological, and self-report). GLMs would be used in which the outcome variable is regressed simultaneously onto the FC cluster, L-DOPA group, dopamine gene score, cue, and context. This would be repeated for the separate fear expression indices, with FDR controlling for alpha inflation due to multiple comparisons. These analyses would identify the clusters of voxels whose FC with the VS, DC, and SN/VTA predict enhanced recall on Day 2.

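### The connectivity-to-recall step of Aim 2 is run only in clusters that survive the whole-brain L-DOPA x gene score map, and the plan has no fallback if none survives

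*Combined protocol and SAP*

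**What the plan says.** The Aim 2 hypothesis in B. Specific Aims has two steps: "The L-DOPA x dopaminergic gene score will predict enhanced post-extinction dopaminergic functional connectivity, which in turn predicts enhanced fear extinction recall".

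G. Statistical Plan, under Data analysis, handles them in sequence.

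- **Step 1, dopaminergic manipulation to FC.** FC maps from three seeds (SN/VTA, dorsal caudate, ventral striatum) are analysed by group and gene score in a "between-subjects ANOVA in a whole-brain, mass univariate, approach". On multiplicity it says "Cluster-level thresholding would be used to correct for multiple comparisons". Neither the cluster-forming nor the corrected p-value is given.
- **Step 2, FC to recall.** This starts "Following identification of regions where FC with the DC, VS, and SN/VTA differ as a function of the L-DOPA x gene score interaction", and then "we would then test whether individual differences in FC within these clusters predict subsequent consolidation of fear extinction learning". Step 1 also maps main effects, but only interaction clusters are carried into step 2.

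The plan does not say what happens if the interaction map is empty, and it defines no seed-to-target FC value in advance.

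Three other places bear on this. A. Benefit to Society and Purpose reports that, in a cited study of healthy adults given L-DOPA, resting-state connectivity "between the ventral tegmental area (VTA) and mPFC was correlated with magnitude of mPFC recruitment during recall of the fear extinction learning". The seed for that connection is fixed in the resting-state section ("SN/VTA; MNI X, Y, Z coordinates = -8, -18, -20 mm"). The section on ROI definition lists six a priori regions ("bilateral amygdala, bilateral hippocampus, ventromedial PFC, dorsal anterior cingulate cortex"), but for task activation, not for connectivity.

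**The concern.** The FC variable in the step 2 models exists only if a voxelwise interaction passes a whole-brain filter. This has two consequences.

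- **Empty map.** There is no FC predictor, so the FC-to-recall models cannot be fitted. The link from connectivity to Day 2 responding, and so mediation, is left unexamined, although every participant has usable FC maps. A target chosen after seeing an empty map would be post hoc.
- **Non-empty map.** The clusters were selected because their interaction was large, so the interaction estimated in the same data overstates the first half of the path.

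At stake is whether the mediating half of one of the trial's two specific aims gets an answer.

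**Working it through.** **Inputs.** N = 105, 35 per group (G. Statistical Plan, power paragraph). Gene score scored 0 to 5 and written as a six-level factor (FC analysis). Alpha, the test behind the power statement, numeric effect sizes and the cluster-forming p are not stated. I assume alpha .05, voxel thresholds of .005 and .001, all 18 group-by-score cells filled, and no lost scans.

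**Formula.** Power = P(F′ > F_crit), where F′ is noncentral F with df1, df2 and noncentrality λ = f² × N.

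**The plan's own power figures.** For a three-group F test (df 2, 102), f = .40 gives .96, consistent with more than .9 for large effects. Power reaches .80 at f = .307, a plausible reading of medium-large. The plan's statement is therefore credible, although it cannot be reproduced exactly without an effect size. I use f = .31.

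**Interaction at one location.** λ = .31² × 105 = 10.09.

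- Gene score as a numeric term: df1 = 2, df2 = 105 − 6 = 99.
- Gene score as six levels: df1 = (3 − 1) × (6 − 1) = 10, df2 = 105 − 18 = 87.

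| Test level | f = .31, 2 df | f = .31, 10 df | f = .25, 2 df | f = .25, 10 df |
|---|---|---|---|---|
| .05 (one pre-specified connection) | .81 | .50 | .61 | .32 |
| .005 (assumed voxel threshold) | .50 | .18 | .28 | .09 |
| .001 (assumed voxel threshold) | .31 | .08 | .14 | .03 |

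These are single-location figures. They do not give the chance that some cluster survives in any of three whole-brain maps. The .05 row is before any FDR adjustment; at .01 the f = .31, 2-df figure is .59.

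**Selection.** With df 2, 99 the critical F at .001 is 7.41, so a location passes only if its observed f is at least √(2 × 7.41 / 99) = .39. When the true f is .31, the median observed f in simulated draws from the noncentral F is about .44 among those that pass, against about .34 without selection.

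**Size of the second step.** Planned Fear Extinction Analyses lists 3 neural, 3 physiological and 2 self-report indices: 3 + 3 + 2 = 8 recall models for each FC measure.

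**The case against.** A reader might infer more than the documents support, and several counter-arguments stand.

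- **That an empty map means no test of Aim 2.** This goes too far. The map tests the effect of L-DOPA and gene score on FC, and the plan presents it as the evidence that the intermediate mechanism is engaged. Only the FC-to-recall step, and hence mediation, is lost.
- **That the protocol already names midbrain-mPFC as its target.** It does not. That connection appears in the background as a cited result. Aim 2 speaks of dopaminergic connectivity in general, and the three seeds are not ranked. The background says mPFC, while the listed ROI is vmPFC, which is intended for task activation and has its coordinates referred to the literature. Choosing this pair is a reasonable proposal, not something the plan has already decided.
- **That the screen is shown to have low power.** The comparison sets one location at a strict threshold beside one region at .05. It depends on an assumed threshold (.59 at .01, .50 at .005, .31 at .001 for f = .31, 2 df) and on the true effect lying in the chosen region. It is not cluster-level power.
- **That a pre-specified connection cures the problem.** Only in part. With the six-level score its power is .50 at f = .31 and .32 at f = .25, so a null result there would also be weak evidence.
- **That selection biases the recall test in the same way.** Inflation applies to the interaction estimate. The recall models use a different outcome, so they do not re-test the selecting statistic.

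None of this supplies the missing fallback.

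**Conclusion.** The point holds in a limited form. Step 2 of Aim 2 depends on a significant interaction cluster, and the plan does not say what is done without one. That is a structural gap, read directly from the text, and it needs no power calculation. The figures are illustrative: under the stated assumptions, a real interaction of f = .31 could readily be missed at any one location, so an empty map should not be read as absence of mediation. How probable an empty map is cannot be derived from the documents. If clusters do survive, their interaction estimates should not be taken at face value. The matter is worth correcting before the FC analysis begins, but it does not invalidate the whole-brain approach.

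**What to change.** Before the FC analysis:

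1. Define one value per participant: the SN/VTA seed map (r-to-z scale) averaged over the vmPFC ROI, with the ROI coordinates written into the plan. Give the cited midbrain-mPFC result as the reason for the choice.
2. Test this value for the L-DOPA x gene score interaction, and as a predictor of each Day 2 index, whatever the whole-brain map shows.
3. Enter the gene score as a numeric term in this test. Otherwise power at f = .31 falls from .81 to .50.
4. Keep the three-seed whole-brain maps and the cluster-based recall models as planned, so that dorsal caudate and ventral striatum effects remain covered. State the cluster-forming and corrected p-values, and report cluster interaction estimates as subject to selection.

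**Cost.** No new scanning is needed; one value is extracted from each map already planned. The FDR family gains one interaction test and about eight recall models, so its adjustment becomes somewhat stricter.

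**Limit.** This ensures that both steps of the path are tested, but it adds no test of the indirect effect. The recall model as described has neither such a test nor a group x gene score term, and that needs its own decision.

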Genetic variation is a primary contributor to individual differences in baseline dopamine neurotransmission (Cools & D’Esposito 2011; Frank and Fossella 2011). Individuals with specific alleles in genes coding for high baseline dopamine demonstrate better performance on tasks probing working memory, cognitive control, and social cognition (Diamond et al. 2004; Egan et al. 2001; Meyer-Lindenberg et al. 2005). Genetic variants in baseline dopamine neurotransmission would therefore be expected to modulate performance-enhancing effects of L-DOPA, such that individuals with low endogenous would be expected to have increased performance upon exogenously increasing dopamine neurotransmission; whereas individuals with high endogenous dopamine would be expected to have performance deteriorate from exogenously increasing dopamine neurotransmission. In support of this hypothesis, a recent study found an interaction between L-DOPA administration and endogenous dopamine neurotransmission (as indicated by a polygenic score pooled across COMT, DAT, DRD1-3) on motor learning performance, such that individuals with a combination of alleles coding for higher baseline dopamine demonstrated a weaker learning benefit from L-DOPA, whereas individuals

**PI:** [name].

with a combination of alleles coding for lower baseline dopamine demonstrated a stronger learning benefit from L-DOPA (Pearson-Fuhrhop et al. 2013). These data demonstrate the non-linear relationship between performance and dopamine levels, suggesting that any investigation of potential effects of boosting dopamine neurotransmission as a means of boosting learning needs to account for baseline dopamine neurotransmission.

Overall, the proposed project seeks to demonstrate the engagement of post-extinction dopamine neurotransmission and downstream acute reorganization of dopaminergic resting-state neural networks as a means of increasing consolidation of generic fear extinction learning in adult women with PTSD.

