## **C. Study Design**

*Overview.* There are three main stages to this experimental protocol: 1) Assessment, 2) Day 1 fMRI, and 3) Day 2 fMRI. Participants would complete these stages across 2-3 days, depending on participant need. Day 1 fMRI and Day 2 fMRI will always be consecutive days.

During the Assessment stage, participants would undergo a structured clinical interview to assess trauma history and mental health diagnoses (See Assessments Section). The assessment stage lasts 3-4 hours.

During Day 1 fMRI, participants would complete ~40 min fMRI scan, then ingest a pill (placebo, 100mg L-DOPA, or 200 mg L-DOPA) upon leaving the scanner and wait in a waiting room for ~45 minutes. Participants then complete the Side Effect Checklist to assess for any drug-related side effects. The participant would then undergo a 7 min resting-state fMRI scan, which concludes Day 1 fMRI. Day 2 fMRI lasts about 2 hours.

Participants return ~24 hours later for Day 2 fMRI, in which they first complete the Side Effect Checklist again and then complete a single ~40 minue fMRI scan. Day 2 fMRI lasts about 1 hour.

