### *Clinical Trial Procedures*

L-DOPA

*Administration.* Prior to pill ingestion, participants would undergo a standardized medical exam (see attached physician screening form) with a study physician to rule out medical and pharmacological contraindications for L-DOPA prescription. Upon passing the medical exam, the study physician would write a prescription to the UW research pharmacy, who maintains the blind, to dispense to our research staff the correct pill. Participants would be randomized to receive either a placebo, 100mg (with 25 mg carbidopa to inhibit peripheral decarboxylase), or 200mg (with 50 mg carbidopa to inhibit peripheral decarboxylase) pill of L-DOPA (see below for randomization and blinding procedures).

The study drug is prepared and maintained by the research pharmacy. Medication is put into two gel capsules, which are identical across the dose ranges of placebo, 100mg and 200mg. Medication kits are prepared separately for the three groups and stored in the locked nurses office of WisPIC along with the study logs of drug administration and allocation for each subject (e.g., subject 001, allocated to group 'blue', provided dose on 2/18/17). There is no washout period required for this study, though participants are required to have been stable on previous medications for at least 4 weeks. Use of MAO-I in past two weeks is exclusionary. As noted above, physician evaluation is performed prior to prescription being written. Participants are assessed for side-effects after 40-min and again 24-hours later.

*Justification and Rationale for L-DOPA Dose Choices.* The dose of 100 mg is consistent with prior studies of L-DOPA on learning as a dose optimizing the inverted U-shaped curve for the dopamine/performance relationship, while the dose of 200 mg is chosen as a suprathreshold dose that establishes the upper bound of the inverted U curve of the dopamine/performance relationship (Monte-Silva, Liebetanz, Grundey, Paulus, & Nitsche 2010; Thirugnanasambandam, Grundey, Paulus, & Nitsche 2011). We chose 200 mg as the suprathreshold dose, as opposed to 300 mg or 500 mg, in order to keep the dose small enough to not inadvertently break the blind (i.e., higher L-DOPA doses are more likely to result in side effects such as dizziness, nausea, fatigue, etc.), and 200 mg has been successfully used in prior learning studies as a suprathreshold dose.

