**PI: [name].**

et al. 2006). In urn randomization, an algorithm modifies ongoing randomization probabilities based on prior composition of treatment groups, maximizing multivariate equivalence of treatment groups (Wei and Lachin 1988). Thus, urn randomization offers the benefits of balancing allocation of important prognostic variables in treatment groups while still retaining the benefits of random assignment (Stout et al. 1994). Participants will be randomized based on comorbid diagnoses, age, and current medication usage.

*Implementation.* The “urn” randomization will be implemented by a department statistician, who will have no direct contact with the participants and no knowledge of the pill assignment to the group labels and thus has negligible chance of biasing the randomization sequence or implementation.

*Blind Assessors.* The clinical research coordinators performing the assessments will be blind to the treatment conditions; thus minimizing the possibility of systematically biasing the assessment procedures.

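### Aim 2's connectivity–recall link is observational, and covariates that enter only when arms differ cannot remove confounding within arms by Day 1 extinction or PTSD severity

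*Combined protocol and SAP*

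**What the plan says.** Section B states Aim 2 as a test of the degree to which "post-extinction functional connectivity within dopaminergic neural networks mediates the effect of dopaminergic manipulation on fear extinction learning". Section A describes the mechanism as "downstream acute reorganization of dopaminergic resting-state neural networks".

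Only the pill is assigned at random: "Participants would be randomized to receive either a placebo" or one of two L-DOPA doses (Clinical Trial Procedures). The urn procedure balances three things: "Participants will be randomized based on comorbid diagnoses, age, and current medication usage". Neither resting FC nor Day 1 learning is among them.

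On Day 1 (Section C, Overview), women complete the task scan, "then ingest a pill (placebo, 100mg L-DOPA, or 200 mg L-DOPA) upon leaving the scanner and wait in a waiting room for ~45 minutes". After the side-effect check, "The participant would then undergo a 7 min resting-state fMRI scan, which concludes Day 1 fMRI". No resting scan before the pill is described.

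In Section G, the paragraph on altered resting-state FC and consolidation first takes the regions whose FC depends on the L-DOPA × gene score interaction. In those regions, "we would then test whether individual differences in FC within these clusters predict subsequent consolidation of fear extinction learning". Each Day 2 index is regressed on FC, group, gene score, cue and context, with FDR across indices.

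Day 1 responding and severity are handled conditionally elsewhere in Section G. The Aim 1 framework adds Day 1 differences where needed, and the MANOVA paragraph adds factors that differ between groups. The FC model adds covariates if the urn procedure "should fail to match groups on demographic and clinical severity variables".

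**The concern.** Randomisation protects two comparisons: pill on FC and pill on recall. It does not protect the comparison of women with higher and lower FC, which is what the link model makes. A woman who extinguished well on Day 1, or whose PTSD is milder, may differ in both post-extinction FC and Day 2 recall, in the same way in every arm.

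The covariate rules look for imbalance between arms, but a confounder of FC and recall need not be imbalanced. A perfectly balanced trial would trigger no Day 1 or severity adjustment and would keep all of this bias.

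At stake is the central Aim 2 claim. A pre-existing difference between women could be read as the route by which dopamine improves extinction recall.

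**Working it through.** **The plan's own figure.** Section G states power above .9 for large effects and about .8 for medium-large effects with 35 per group (N = 105). Effect sizes and alpha are not given, so I assume two-sided .05. For a three-group ANOVA, λ = N f². With f = .40, λ = 105 × .16 = 16.8 and power is .96. With f = .31, λ = 105 × .0961 = 10.1 and power is .807. For two arms of 35, d = .80 gives .91 and d = .68 gives .801. The statement reproduces, but for drug-group effects. The plan gives no figure for the FC–recall link.

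**Size of a spurious link.** Suppose a variable correlates a with FC and b with recall, and FC has no effect on recall. The induced correlation is a × b. With N = 105 and three covariates (two group terms and gene score), Fisher's z has standard error 1/√(105 − 3 − 3) = 1/√99, so the rejection rate is about Φ(√99 · atanh(ab) − 1.96), plus a negligible lower tail.

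- 0.3 × 0.3 = 0.09: about 15%
- 0.4 × 0.4 = 0.16: 9.95 × 0.161 − 1.96 = −0.35, about 36%
- 0.5 × 0.5 = 0.25: 9.95 × 0.255 − 1.96 = 0.58, about 72%

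These rates ignore the interaction step, so they do not describe the planned procedure.

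**Adding the interaction step.** Simulation assumptions were:

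- N = 105, with one recall score per woman and gene score Binomial(5, .5);
- a real drug × gene effect on FC of 0.3 per gene-score point, in opposite directions at the two doses;
- no effect of FC on recall;
- Day 1 extinction measured with reliability .8.

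Only trials with an interaction p < .05 go forward (about two thirds). Among them, the FC term is significant as follows:

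| Confounder | Loading on FC and on recall | Planned model | Day 1 extinction always entered |
|---|---|---|---|
| None | 0 | 4.6% | 4.8% |
| Day 1 extinction | 0.3 | 15.0% | 5.5% |
| Day 1 extinction | 0.5 | 67.9% | 9.1% |
| Day 1 extinction | 0.7 | 100% | 32.7% |
| Stable trait | 0.3 | 13.5% | 13.9% |
| Stable trait | 0.5 | 69.5% | 69.3% |
| Stable trait | 0.7 | 99.9% | 99.9% |

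Selecting clusters on the interaction hardly changes the false-link rate (69.5% against 72.5% ungated, stable trait at 0.5), because the FC coefficient rests largely on differences within arms. The stable-trait rows show that Day 1 extinction does not help against a trait unrelated to it. That is the reason for also entering severity, although the gain from CAPS was not simulated.

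**Pre-pill FC.** If pre- and post-pill FC correlate ρ and each has an induced correlation of .25 with recall, the remaining partial correlation is (.25 − .25ρ)/√((1 − .25²)(1 − ρ²)). For ρ = .25, .5, .7 and .9 this is .20, .149, .108 and .059, and the false-link rate is 54%, 33%, 20% and 9%.

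All loadings, reliabilities and values of ρ are assumptions; the documents give none.

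**The case against.** **The interaction step.** A reader might infer that the link could readily appear with no drug effect on FC at all. The documents do not support that, because the link is tested only in clusters showing the interaction. With no drug effect on FC, 5.3% of simulated trials passed and 71.4% of those showed a link at loadings of 0.5: .053 × .714 = 3.8% per seed, or 1 − (1 − .038)³ = 11% over three independent seeds. This takes the cluster-level alpha as .05, which the plan does not state. What stands is the narrower point: once a cluster passes, the step gives no protection.

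**The test of drug on FC.** A reader might also infer that, without a pre-pill scan, the plan cannot claim an acute drug effect on FC. That does not follow. The pill is randomised, so a post-pill contrast between arms, and its variation with gene score, is a valid test. Stable variance between women costs precision only. With 49% stable variance and no baseline covariate, a simulated null interaction was rejected 4.6% of the time.

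**FDR.** The rates above are for single tests. At the strictest FDR step over the eight indices named in the MANOVA paragraph (.05/8), induced correlations of .09, .16 and .25 give about 3%, 13% and 42%. Confounding shared by several indices would soften that threshold. In any case FDR controls chance findings, not bias.

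**Existing handling and wording.** Section C models medication without condition, and Section G controls for ancestry. The text of the link paragraph is associational; the causal wording is in Aim 2 and in that paragraph's title. This is fair, but no unconditional Day 1 or severity term is stated for the link model, and neither an indirect-effect test nor a sensitivity analysis for confounding is planned.

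**Conclusion.** The point holds in this form: among clusters that pass the interaction step, an FC–recall link can arise within arms from Day 1 extinction or PTSD severity while the drug-induced part of FC contributes nothing to recall. The conditional covariate rules cannot prevent it. The single-test false-link rate is about 70% at assumed loadings of 0.5 and about 15% at 0.3, against a nominal 5%.

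Whether such confounding exists here, and in which direction, cannot be known from the documents. The conclusion concerns what the planned model can support. It does not show that a link, if found, would be false.

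**What to change.** In every link model:

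1. Enter Day 1 extinction responding for that index, whether or not arms differ. Extinction runs in one context only (B), so the Context B value must also serve for Context A outcomes. Self-report ratings are described only in the recall paragraph of the task description. If none exist for Day 1, use a physiological Day 1 extinction index.
2. Enter CAPS severity, also unconditionally. Both covariates precede the pill, so adjusting for them does not remove any drug effect.
3. Add the group × gene score term. It selected the clusters, so without it an effect of that interaction on recall by another route could be credited to FC.

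Report FC-to-recall as an adjusted association, not as mediation. Give a sensitivity analysis for residual confounding of FC with recall, for example the a × b needed to explain the result: a partial correlation of .25 needs 0.5 on each side.

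Pre-pill FC could be estimated from Day 1 task residuals as a sensitivity covariate in both the FC and link models. Reading the task description as 12 presentations of each cue per phase, acquisition and extinction give 2 × 24 = 48 trials of 6–9 s, or 4.8–7.2 minutes, close to the 7-minute rest run. This is not a rest scan, so its correlation with post-pill FC is uncertain and it should not be a condition for claiming a drug effect on FC.

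Cost: analysis work with no new visit or scan. The added terms take 1 + 1 + 2 = 4 df with a linear gene score, or 1 + 1 + 10 = 12 df if it has six categories. Day 1 indices rest on few trials and are noisy, so bias is reduced, not removed; even at reliability .8 the table leaves 9% at loadings of 0.5 and 33% at 0.7.
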